## **3.7.3      Pharmacokinetic/Pharmacodynamic Assessments**

### **3.7.3.1      Pharmacokinetic Assessments**

#### **3.7.3.1.1      Blood Collection Times**

Blood samples will be taken so that tolvaptan and metabolite concentrations can be determined. Samples will be taken at the following times:

- On Day 1 at 2 hours ( $\pm 5$  minutes) and 8 hours (concurrent with 8 h serum sodium sample) post-first dose.
- On Days 1, 2, 3, and 4 samples will be taken at trough ( $24 [\pm 4]$  hours post-previous dose) (prior to the subsequent dose), concurrent with serum sodium samples, for subjects dosed with tolvaptan on Days 1, 2, 3, and 4, respectively, regardless of status as responder/nonresponder.
- An early termination (ET) sample will be taken for any subject who is receiving tolvaptan.

On Day 2a no PK samples are taken.

For each PK blood sample collected volumes are not expected to exceed 1.2 mL. Total volume per sample may be lower depending on finalization of blood collection supplies.

Serum sodium assessments and other clinically necessary blood samples take priority; therefore, due to restrictions in allowable total daily blood volumes based on local guidelines and subject age, it may not be possible to take more than one PK sample per day. If so, the PK sampling should be changed to:

- Day 1: 2 hours postdose ( $\pm$  5 minutes)
- Day 2: 8 ( $\pm$  2) hours postdose (may be concurrent with serum sodium or other blood sampling)
- Day 3 at trough, ie, predose/24 hours post prior dose (concurrent with serum sodium sample)
- Day 4 at trough, ie, predose/24 hours post prior dose (concurrent with serum sodium sample)

The PK profiles will be evaluated on an ongoing basis to determine the variability between subjects. Based on the findings, PK sampling will continue for as long as necessary to establish suitable estimates of clearance with a 90% CI similar to that observed in the adult populations. Once these estimates are achieved, sampling will be discontinued in subsequent subjects.

For each subject all samples will be collected according to local guidelines and best practices for pediatric care. If a sample is missing due to limitations in allowable blood volumes based on local regulations or local practice this will not count as a protocol deviation.

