#### **7.4.2.3 Pharmacokinetic Parameters**

Previously obtained PK data from 81 adult subjects who received a 30-mg dose of tolvaptan will be included in the analysis to show the similarity for PK parameter estimates between adult and pediatric subjects. An analysis of variance model will be performed on the natural-log transformed PK parameters using the MIXED procedure in SAS, in which only one fixed effect of subject group (pediatric and adult groups) is included in the model. The anti-logs of the difference of LS means and the confidence limits will provide the estimate and 90% CI for the ratio of the geometric means of pediatric group and adult group. Similarity of a PK parameter between pediatrics and adults will be indicated if the 90% CI for the ratio of the population geometric means is contained within the equivalence limits of 0.6 to 1.4.

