4.2 Sample Size for Pharmacokinetic Parameters

The sample size to establish similarity between the confidence intervals (CIs) for PK parameter estimates in adults and pediatrics is based on PK data of clearance.

To be conservative, it is assumed that the coefficient of variation (CV) of clearance is 0.42. In order to establish a 95% CI within 60% and 140% of the point estimate for the geometric mean estimate of clearance in an age group (age < 10 or \geq 10 years), under the assumption that the geometric mean estimates of clearance are equal between adult and pediatric subjects, CIs of the ratio of geometric means of pediatrics and adults will be constructed. Twenty pediatric subjects and 80 adult subjects are needed to have 90% power to establish a 95% CI of the ratio of geometric means within 0.71 and 1.40. In the actual analysis, all 81 adult subjects' data will be used.

5 Statistical Methods

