5.1.10 Analysis of Pharmacokinetic Parameters

To establish similarity between the CIs for PK parameter estimates between adults and pediatrics based on PK data of clearance, the clearance data of at least 20 pediatric subjects from this trial and 81 adult subjects from an existing tolvaptan trial will be used. An analysis of variance model will be performed on the natural log transformed PK parameters using the MIXED procedure in SAS, in which only one fixed effect of subject group (pediatric and adult groups) is included in the model. From each analysis, least squares means, their difference, and the 90% CI for their difference will be derived.

Then, the antilogs of the difference and the confidence limits will provide the estimate and 90% CI for the ratio of the geometric means of the 2 treatments (pediatric vs adult).

The similarity of PK parameter estimates between adults and pediatrics will be claimed if the 90% CI for the ratio of the population geometric means—based on the analysis of the log-transformed data—is contained within the confidence limits of 0.60 to 1.40.

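### The PK comparison is sized for clearance within an age group, but the analysis pools all children, so similarity to adults is not formally tested in either age group

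*SAP*

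**What the plan says.** **Sizing.** SAP 4.2 and protocol 7.1.2 aim at "the geometric mean estimate of clearance in an age group", the groups being under 10 years and 10 years or older. The assumed CV of clearance is 0.42 and the assumed true ratio is 1. The result is that "Twenty pediatric subjects and 80 adult subjects are needed to have 90% power" for a "95% CI of the ratio of geometric means within 0.71 and 1.40". Neither section prints 20 per age group or a total of 40.

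**Analysis.** SAP 5.1.10 asks for at least 20 children from this trial and 81 adults from an existing trial. It fits log-transformed parameters and says that "only one fixed effect of subject group (pediatric and adult groups) is included in the model". Similarity is claimed if the 90% CI for the ratio of geometric means lies within 0.60 to 1.40. Protocol 7.4.2.3 gives the same model and limits. Neither section has an age-group term, a ratio per age group or a minimum per age group.

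**Other age analyses.** Protocol 6.1 summarises Day 1 PK parameters by dose group and age group, plans to assess effects of age, sex, race and disease state, and refers to a separate population analysis.

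**Stopping PK sampling.** The protocol synopsis and 3.7.3.1.1 have PK reviewed during the trial for between-subject variability. Sampling continues until clearance is estimated with a 90% CI similar to that in adults. "Once these estimates are achieved, sampling will be discontinued in subsequent subjects". No number, look schedule or adjustment is given.

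**Early termination.** SAP 5.1 reduces the efficacy analyses to summary statistics. Section 5.1.10 sits under that heading, but PK is not named.

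**The concern.** The sizing and the analysis answer different questions. The sizing asks whether clearance within an age group resembles adult clearance. The analysis asks whether the average over all children does. That average depends on which children happen to supply PK samples, and it can lie well inside the limits when one age group does not. Protocol 2.1 gives possible differences in absorption, distribution, metabolism and elimination as the reason for taking PK samples in children. Protocol 2.1.1 notes that CYP3A is lower at birth and reaches adult levels by 2 years. A single pediatric mean is weakest where age is expected to matter.

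At stake are a similarity claim that could be read as covering both age groups when neither was tested, and lower power within each group than the sizing section implies.

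**Working it through.** **Inputs.** CV 0.42, 20 children, 80 adults, true ratio 1, and a 95% CI within 0.71 to 1.40 (SAP 4.2); 81 adults, and a 90% CI within 0.60 to 1.40 (SAP 5.1.10). Log-scale SD = √ln(1 + 0.42²) = 0.403. SE of the log ratio = 0.403 × √(1/n + 1/m), for n children and m adults. Power is that of two one-sided t-tests, integrated over the distribution of the pooled variance.

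**1. The plan's own figure.** For 20:80, SE = 0.403 × √(1/20 + 1/80) = 0.1008.

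| CI and limits | Power, 20:80 | Children needed for 90% |
|---|---|---|
| 95% CI, 0.71–1.40 (as written) | 83.1% | 25 |
| 90% CI, 0.71–1.40 | 91.1% | 20 |
| 95% CI, 0.60–1.40 | 91.0% | 20 |

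The stated 20:80 at 90% power is reproduced if either the CI level or the lower limit is changed to the value in SAP 5.1.10, but not as written.

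**2. Power in one age group under the SAP 5.1.10 rule** (90% CI, 0.60–1.40, 81 adults, true ratio 1; ln 0.60 = −0.511, ln 1.40 = 0.336).
- n = 20: SE = 0.1006, t = 1.660, half-width 0.167. The estimate must fall between −0.344 and 0.169. Power is 95%.
- n = 10: SE = 0.1351, t = 1.662, half-width 0.225. The estimate must fall between −0.286 and 0.112. Power is 78%.
- Two groups of 20 sharing the same adults: about 91% that both pass.

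**3. What pooling does when the younger group is at a limit.** Assume a ratio of 1.0 in the older group. With equal numbers the pooled true ratio is the geometric mean of the two: √0.60 = 0.775 (log −0.255) or √1.40 = 1.183 (log 0.168).
- 10 + 10, half-width 0.167. For 1.40: (0.169 − 0.168)/0.1006 ≈ 0.01, so about 50%. For 0.60: (−0.255 + 0.344)/0.1006 ≈ 0.88, so about 81%.
- 20 + 20, SE = 0.0779, half-width 0.129. For 1.40: (0.207 − 0.168)/0.0779 ≈ 0.50, so about 69%. For 0.60: (−0.255 + 0.382)/0.0779 ≈ 1.63, so about 95%.

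Simulation also allows for the extra spread that mixing two groups puts into the pooled SD:

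| Younger + older | Passes, younger ratio 0.60 | Passes, younger ratio 1.40 |
|---|---|---|
| 10 + 10 pooled | 79% | about 50% |
| 20 + 20 pooled | 93% | 68% |
| 5 + 15 pooled | 98% | 79% |
| Age-group test, 20 younger | 5% | 5% |

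Enrolling more children makes the pooled pass more likely, because the pooled ratio lies inside the limits.

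**4. The stopping rule under two readings** (same true ratio in all children, at a limit).
- Stop when the ratio CI first lies within 0.60–1.40, looking from n = 20: false similarity about 8% (looks at 20 and 40), 11% (every 10 up to 70) or 16% (every child up to 100).
- Stop on CI width alone and test once afterwards: 4.9% to 5.5%.

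**The case against.** **Age is not ignored.** Protocol 6.1 plans age-group summaries, an age-effect assessment and a population analysis. Suppose the ratio is 0.55 in 10 younger children and 1.0 in 10 older ones. This is an illustrative value, and the form of age test is also assumed, since protocol 6.1 names none. The pooled test passes 64% of the time, but a plain comparison of the two age groups is significant 88% of the time. Only 8% of runs pass the pooled test and show no age effect. This stands: a reader who infers that age goes unexamined is wrong. But none of these analyses carries a similarity criterion or prevents the pooled claim.

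**Twenty per group is a reading, and at least 20 is a floor.** Protocol 3.7 samples all subjects until PK data are adequate, about 100 are planned, and protocol 3.3 wants at least half of those enrolled to be under 10. A PK set made up only of older children is therefore remote. That also stands, although the age quota governs enrolment and not the PK set.

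**Ten children meet the precision goal.** SAP 4.2 also asks for a 95% CI within 60% to 140% of the estimate in an age group. With 10 children, exp(±2.262 × 0.403/√10) gives 0.75 to 1.33, which is inside. The shortfall is in power for similarity, not in this precision target.

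**Stopping on success.** A reader might infer that sampling stops once similarity is reached, so that the 5% error is inflated. The text does not support this as fact. The reviews are for between-subject variability, and the stopping text names neither the pediatric/adult ratio nor 0.60 to 1.40. Read as a precision rule, it keeps the error near 5%. What remains is that the criterion is not defined.

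**Conclusion.** The mismatch is real. The comparison is sized within an age group but analysed on one pooled pediatric mean, so age-group similarity is not formally tested. At CV 0.42 with 81 adults and a ratio of 1.0 in older children, a younger group at the edge of the limits passes the pooled 10 + 10 test about 79% (0.60) or 50% (1.40) of the time, instead of 5%. Power with 10 children in a group is 78%, against 95% with 20. These figures depend on the age split of the PK set, which the plan does not fix, and on the assumed ratios, which are not predictions.

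Inflation through the stopping rule is conditional: about 8% to 16% if the rule is applied to the ratio, and about 5% if applied to CI width. Separately, the sizing as written gives about 83% power, not 90%.

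Early termination and very low enrolment limit the practical weight. The SAP does not say whether the PK claim survives the reduction to summary statistics, and SAP 5.1.10 still sets out when similarity will be claimed.

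**What to change.** 1. In SAP 5.1.10 and protocol 7.4.2.3, replace the two-level factor with three levels: adult, under 10 years, 10 years and older. Give the ratio and 90% CI for each age group against adults, and claim similarity per age group.
2. In SAP 5.1.10, change the minimum of 20 children to at least 20 with evaluable clearance in each age group. If early termination leaves fewer, report ratios and CIs descriptively and make no similarity claim.
3. In the protocol synopsis and 3.7.3.1.1, state that sampling stops on the per-group count or on a stated CI width, and not on the pediatric/adult ratio.
4. Reconcile the 95% CI within 0.71 to 1.40 in SAP 4.2 and protocol 7.1.2 with the 90% CI within 0.60 to 1.40 in SAP 5.1.10 and protocol 7.4.2.3, and restate the power for the pair chosen.
5. State in SAP 5.1 whether the reduction to summary statistics covers PK.

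The cost is mostly wording, and age is already recorded. Twenty per group means 40 of about 100 planned children, so some may give PK samples who would not have done so under an earlier stop. In the terminated trial, only the analysis and reporting changes still matter.

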5.2 Safety Analysis

The safety analysis will be conducted based on the Safety Samples, which are defined in [Section 5.1.1](#). Safety variables to be analyzed include adverse events (AEs), clinical laboratory data, and vital signs. In general, summary statistics will be provided for safety variables based on all available data.

Safety analyses will be performed for Treatment Phase A and Treatment Phase B separately. Safety analyses by age categories [REDACTED]
[REDACTED] will be provided as well.

5.2.1 Duration of Exposure to Trial Medication

Duration of exposure to each treatment of each subject will be summarized by treatment group. A subject's duration of exposure is defined as the IMP end date – IMP start date + 1.

5.2.2 Adverse Events

Definitions:

- A treatment-emergent adverse event (TEAE) is an event that is observed or reported after administration of IMP in this trial that was not present prior to IMP administration or an event that represents the exacerbation of a pre-existing event. Exacerbation includes any event that increases in frequency or severity or becomes classified as serious after the start of treatment in this trial.
- An adverse withdrawal is a subject who withdrew from the trial due to an AE.
- A serious adverse event (SAE) is an AE that is classified as serious according to the criteria specified in the trial protocol.

Safety variables of analysis include:

- Proportion of subjects with TEAEs
- Proportions of subjects with TEAEs by preferred term
- Proportion of subjects with severe TEAEs
- Proportion of subjects with serious TEAEs
- Proportion of subjects with TEAEs leading to death
- Proportion of subjects with potentially drug-related TEAEs
- Proportion of subjects with TEAEs that result in trial termination

Analysis of special interested AEs include:

- Proportion of subjects with absolute serum sodium level \geq 145 mEq/L
- Proportion of subjects with overly rapid rise in serum sodium defined as an increase in serum sodium of [REDACTED] or a rate of increase in serum sodium that the investigator deems too rapid
- Proportion of subjects with neurological symptoms or other signs or symptoms suggestive of osmotic demyelination
- Proportions of subjects with worsening symptoms of hyponatremia
- Proportion of subjects with hypovolemia or hypotension requiring intervention

All AEs will be coded by MedDRA (Medical Dictionary for Regulatory Activities) system organ class and preferred term.

5.2.3 Laboratory Test Results

Summary statistics for the clinical laboratory measurements at baseline and postbaseline visits, and summary statistics of changes from baseline to each visit will be presented by treatment group. Shift tables will be produced, assessing low-normal-high (at baseline) to low-normal-high (at postbaseline visit).

The incidence of treatment-emergent potentially clinically significant abnormal laboratory results will also be summarized by treatment groups. Listings of potentially clinically significant abnormalities will also be provided.

According to the Food and Drug Administration (FDA) Guidance,¹ laboratory measurements that signal the potential for drug-induced liver injury (DILI) will be reported. An incidence table and a listing will be provided for subjects who meet one or combinations of the following criteria:

- 1) ALT (alanine transaminase) or AST (aspartate transaminase) $\geq 3x$ upper limit of normal (ULN) (or baseline value for subjects with abnormal baseline)
- 2) Increase in bilirubin $\geq 2x$ ULN (or baseline value for subjects with abnormal baseline)

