#### **Pharmacokinetic Sampling**

Blood samples for PK analysis will be obtained at 2 and 8 hours post-first dose, and at trough (24 [ $\pm 4$ ] hours post-previous

dose) on Days 1, 2, 3, and 4 for all subjects dosed with tolvaptan on Days 1, 2, 3, and 4, respectively, regardless of responder status. Pharmacokinetic profiles will be evaluated on an ongoing basis to determine variability among subjects. Based on the findings, PK sampling will continue for as long as necessary to establish suitable estimates of clearance with a 90% confidence interval (CI), similar to that observed in adult subject populations. Once these estimates are achieved, sampling will be discontinued in subsequent subjects in order to minimize blood draws in this pediatric population.
	
Subject Population:	
This trial will enroll approximately 100 male and female subjects to get approximately 70 randomized subjects aged <math>\geq</math> 4 weeks (or <math>\geq</math> 44 weeks adjusted gestational age) to < 18 years who have been diagnosed with euvolemic or hypervolemic hyponatremia (<math>< 130</math> mEq/L [mmol/L]) that persists despite initial standard background therapy (including fluid restriction and excluding a vasopressin antagonist). Age groups will be enrolled such that at least 50% of these subjects will be < 10 years old and at least 25% of subjects < 6 years old.
 
Subjects with acute hyponatremia or hyponatremia expected to resolve spontaneously will be excluded from the trial. Children with an impaired ability to sense or communicate their thirst will either be required per protocol to undergo closer in-hospital observation, laboratory and urine output monitoring, or will be excluded from the trial if this is not possible.
 
The protocol entry criteria have been designed to ensure careful selection of subjects with chronic (<math>\geq</math> 48 hours) dilutional hyponatremia (euvolemic or hypervolemic) associated with heart failure, hepatocellular disease (including cirrhosis), or syndrome of inappropriate secretion of antidiuretic hormone/other, who may benefit from treatment with tolvaptan, while excluding those who have acute or transient hyponatremia, have overt symptoms of hyponatremia requiring immediate intervention, or who are at increased risk for developing hyponatremic encephalopathy or osmotic demyelination.

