**Table 3.4.3-1      Exclusion Criteria**

Table 3.4.3-1 Exclusion Criteria	
8.	Has eGFR < 30 mL/min/1.73 m  calculated by the following equation: eGFR (mL/min/1.73 m  ) = 0.413 × height (cm)/serum creatinine (mg/dL)
9.	Has AKI defined as: 
 
• Increase in serum creatinine by ≥ 0.3 mg/dL (≥ 26.5 µmol/L) within 48 hours; or
 
• Increase in serum creatinine to ≥ 1.5 times baseline, which is known or presumed to have occurred within the prior 7 days; or
 
• Urine volume < 0.5 mL/kg/h for 6 hours
 

10.	Has severe or acute neurological symptoms requiring other intervention (eg, hyperemesis, obtundation, seizures)
11.	Has had treatment for hyponatremia with: 
 
• Hypertonic saline (including normal saline challenge) within 8 hours of qualifying serum sodium assessments;
 
• Urea, lithium, demeclocycline, conivaptan, or tolvaptan within 4 days of qualifying serum sodium assessments;
 
• Other treatment for the purpose of increasing serum sodium concurrent with dosing of trial medication
 

12.	Has anuria or urinary outflow obstruction, unless the subject is, or can be, catheterized during the trial
13.	Has a history of drug or medication abuse within 3 months prior to Screening or current alcohol abuse
14.	Has a history of hypersensitivity and/or idiosyncratic reaction to benzazepine or benzazepine derivatives (such as benazepril)
15.	Has psychogenic polydipsia (subjects with other psychiatric illness may be included per medical monitor approval)
16.	Has uncontrolled diabetes mellitus, defined as fasting glucose > 300 mg/dL (16.7 mEq/L [mmol/L])
17.	Has screening liver function values > 3 × ULN
18.	Subjects who have cirrhosis and meet any of the following conditions: a major GI bleed within the past 6 months, evidence of active bleeding (eg, epistaxis, petechiae/purpura, hematuria, or hematochezia), platelet count < 50,000/µL, or use of concomitant medications known to increase bleeding risk
19.	Has hyponatremia due to the result of any medication that can safely be withdrawn (eg, thiazide diuretics)
20.	Has hyponatremia (eg, hyponatremia in the setting of adrenal insufficiency, untreated hypothyroidism, or hypotonic fluid administration) that is most appropriately corrected by alternative therapies
21.	Is currently pregnant or breastfeeding

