### **5.4.1 Liver Transaminase Elevations**

Management of abnormal liver function test results should be based on the investigator's clinical judgment. A liver function test result that is  $2 \times$  ULN is generally accepted as a medically significant occurrence across various medical disciplines.

For a subject that experiences an elevation in AST or ALT that is  $\geq 2 \times$  ULN or whose levels increase  $\geq 2$  times their initial baseline value in subjects with an elevated baseline value, a total bilirubin level should also be evaluated. If the total bilirubin is  $\geq 2 \times$  ULN or  $\geq 2$  times their baseline value in subjects with an elevated baseline value, an IRE form with all values listed should be completed and also reported as an AE on the eCRFs.

The following guideline for repeat testing may be used by investigators as a reference for any subject with an ALT or AST  $\geq 2 \times \text{ULN}$ :

- 1) ALT, AST, alkaline phosphatase, and total bilirubin should be repeated within 48 to 72 hours (needed to confirm abnormalities and determine if they are increasing or decreasing).
- 2) Inquiries should be made about symptoms (fatigue, nausea, vomiting, right upper quadrant pain or tenderness, fever, and/or rash) and signs like jaundice, yellowish discoloration of sclera, etc.
- 3) If discharged or transferred, the subjects should be retested locally and results given to the investigator immediately, along with that laboratory's normal ranges.
- 4) Close observation is required if symptoms persist or repeat testing shows ALT or AST  $\geq 3 \times \text{ULN}$  for subjects with normal baseline measures OR 2-fold increases above baseline values for subjects with elevated values before drug exposure. If close monitoring is not possible, the drug should be interrupted until such monitoring is possible or the drug should be permanently discontinued.
- 5) All trial subjects with evidence of possible drug-induced liver injury should be followed until all abnormalities return to normal or to the baseline state.

Close observation may involve:

- 1) Repeating liver enzymes and serum bilirubin tests 2 or 3 times weekly.
- 2) Frequency of retesting can decrease to once a week or less if abnormalities stabilize or if the trial drug has been interrupted/discontinued and the subject is asymptomatic.
- 3) Obtaining a more detailed history of symptoms and prior or concurrent diseases.

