#### **5.4.1.1 Criteria for Discontinuation Due to Liver Transaminase Elevations**

A subject must be discontinued from the trial on confirmation of any of the following criteria:

- 1) ALT or AST  $\geq 8 \times$  ULN
- 2) ALT or AST  $\geq 5 \times$  ULN for more than 2 weeks
- 3) ALT or AST  $\geq 3 \times$  ULN AND (total bilirubin  $\geq 2 \times$  ULN or INR  $> 1.5$ )
- 4) ALT or AST  $\geq 3 \times$  ULN with appearance of fatigue, nausea, vomiting, right upper quadrant pain or tenderness, fever, rash, and/or eosinophilia ( $> 5\%$ ) and signs of jaundice

If there is any question about how to proceed with a particular subject's case, do not hesitate to contact your regional medical monitor to discuss. The FDA has issued a guidance for industry regarding this topic. This guidance is not specific to hyponatremia. Otsuka is integrating many of the recommendations in this guidance into all of its clinical research programs. Links to this guidance and information from the FDA regarding drug-induced liver injury are provided in the references. 

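### SAP 5.2.3 replaces ULN with baseline when baseline is abnormal, so its liver-injury table can omit some children who meet a mandatory protocol stopping criterion

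*SAP*

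**What the plan says.** **SAP 5.2.3** sets the entry rule for the liver table: "An incidence table and a listing will be provided for subjects who meet one or combinations of the following criteria". There are two criteria. The first is ALT or AST at 3 times the "upper limit of normal (ULN) (or baseline value for subjects with abnormal baseline". The second is bilirubin at 2 times ULN, with the same parenthesis about abnormal baselines.

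**Protocol 5.4.1.1** says: "A subject must be discontinued from the trial on confirmation of any of the following criteria". The four criteria are all stated against ULN, with no adjustment for baseline:
1. ALT or AST at least 8 × ULN.
2. ALT or AST at least 5 × ULN for more than 2 weeks.
3. ALT or AST at least 3 × ULN, with bilirubin at least 2 × ULN or INR above 1.5.
4. ALT or AST at least 3 × ULN, with listed symptoms and signs of jaundice.

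**Protocol Table 3.4.3-1, criterion 17**, excludes a child who "Has screening liver function values > 3 × ULN", so abnormal values up to and including 3 × ULN are eligible. The Synopsis (Subject Population) names the target etiologies as "heart failure, hepatocellular disease (including cirrhosis), or syndrome of inappropriate secretion of antidiuretic hormone/other".

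**Protocol 5.4.1** does use baseline multiples, but for other purposes. For reporting, its transaminase trigger is 2 × ULN or 2 "times their initial baseline value in subjects with an elevated baseline value". For close observation it uses "2-fold increases above baseline values for subjects with elevated values before drug exposure".

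**Protocol 1.3** gives the Hy's Law laboratory criteria against ULN only: ALT or AST above 3 × ULN accompanied by total bilirubin above 2 × ULN.

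**The concern.** The liver table is the SAP's dedicated summary of possible drug-induced liver injury. Its threshold rises with the child's baseline, while the protocol's stopping limits stay fixed. The table is therefore least sensitive in children who enter with raised transaminases, a group that the entry criteria admit and that the hepatocellular etiology makes likely. A clinical study report could describe a child stopped under a liver criterion while the liver table shows no such child. It could also report a combined ALT-plus-bilirubin count that disagrees with the protocol's own Hy's Law definition.

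**Working it through.** The plan states no figure to reproduce here. The check compares thresholds, all in multiples of ULN.

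**Inputs.** Let b be baseline ALT or AST and c baseline bilirubin. Criterion 17 caps both at 3.0 at screening. The scheduled pre-dose chemistry is the screening sample, so I take that as baseline.

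**SAP table rule, read as substitution.** A subject enters if ALT or AST ≥ 3 × max(1, b), or if bilirubin ≥ 2 × max(1, c).

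**Where the ALT/AST threshold passes a stopping limit.**
- 3b > 8 when b > 8/3 = 2.67 (criterion 1)
- 3b > 5 when b > 5/3 = 1.67 (criterion 2)
- 3b > 3 when b > 1 (criteria 3 and 4)

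| Baseline ALT (× ULN) | ALT needed for the table (× ULN) |
|---|---|
| up to 1.0 | 3.0 |
| 1.5 | 4.5 |
| 2.0 | 6.0 |
| 2.5 | 7.5 |
| 2.8 | 8.4 |
| 3.0 | 9.0 |

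**Children who are stopped but absent from the table.**
- *Criterion 1.* Baseline ALT 2.8; on study, ALT 8.2 with normal bilirubin. The stop applies because 8.2 ≥ 8. The table needs 3 × 2.8 = 8.4.
- *Criterion 3 through INR.* Baseline ALT 2.0 and normal bilirubin; on study, ALT 4, bilirubin 1.5, INR 1.6. The stop applies. The table needs ALT 3 × 2.0 = 6.0 or bilirubin 2.0.
- *Criterion 3 with raised baseline bilirubin.* Baseline ALT 2.5 and bilirubin 1.5; on study, 4 and 2.5. The stop applies because 4 ≥ 3 and 2.5 ≥ 2. The table needs ALT 3 × 2.5 = 7.5 or bilirubin 2 × 1.5 = 3.0.

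**A child listed, but missing from the combination.** Baseline ALT 2.0 and normal bilirubin; on study, ALT 5 and bilirubin 2.1. This meets the Protocol 1.3 laboratory values and stopping criterion 3. In the SAP, bilirubin qualifies (2.1 ≥ 2.0) but ALT does not (5 < 6.0), so the child is listed for bilirubin alone.

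**Who cannot be missed.** Every 5.4.1.1 criterion requires ALT or AST of at least 3 × ULN (8, 5, 3 and 3). If the enzyme that triggers the stop was normal at baseline, its table threshold is also 3 × ULN, so the child is in the table. By the same argument, a row at fixed 3 × ULN for all subjects would contain every 5.4.1.1 stop.

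**The case against.** **The route is narrow.** Criterion 1 is missed only for baselines between 2.67 and 3.0 × ULN and on-study values from 8 up to, but below, 3b (at most 9). Criterion 2 needs more than two weeks of elevation in a trial whose last contact is 14 days after the last dose. Chemistry is scheduled only at screening and at 72 hours after the last dose or early termination, so a stop during dosing would usually rest on unscheduled tests. Protocol 3.3 also lists severe liver disease among the ineligible states, and SAP 5.1 records very low enrolment and early termination. All of this stands, and it limits the expected number of cases.

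**Baseline multiples are legitimate.** The protocol uses them itself in 5.4.1, and a fixed 3 × ULN row would list a child who entered at 3 × ULN and never changed. This is a reason to keep the baseline rule, but not to make it the only one.

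**The parenthesis could mean either limit.** Then nobody would be missed. But for a raised baseline, 3 × baseline always exceeds 3 × ULN, so the parenthesis would do nothing. Substitution is the natural reading, and the text should say so.

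A reader might infer more than the documents support:
- *That the table leaves out liver stops and reportable liver events in general.* It does not. Meeting one criterion is enough, so a child stopped on bilirubin from a normal baseline enters through the bilirubin criterion even if ALT is not flagged. Reportable cases under Protocol 5.4.1 also carry a bilirubin condition. If its baseline option is read as substitution too, it matches the SAP's second criterion.
- *That the omitted child is lost from all outputs.* SAP 5.2.2 counts adverse events that end participation, 5.2.3 lists potentially clinically significant values, and 5.2.4 brings unscheduled tests into outlier analyses. These do not close the gap: the first is not specific to the liver, the second states no liver threshold, and the shift tables have only three levels, so a rise within the high range does not show.
- *That the protocol cites a transaminase signal in this population.* The signal in Protocol 1.3 is in adult ADPKD. The hyponatremia and heart failure programs showed no ALT imbalance, although risk is not excluded. Protocol 3.7.4.2.4 puts expected onset at 3 to 14 months of chronic use.

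**Conclusion.** The point holds as a limited reporting gap. Some children with abnormal baseline ALT or AST can meet a mandatory 5.4.1.1 criterion and be absent from the SAP liver table, or be missing from its combined count. The ALT/AST threshold can reach 9 × ULN, against a fixed stop at 8.

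The conclusion rests on three assumptions: that the parenthesis substitutes baseline for ULN, that the screening sample is the baseline, and that the bilirubin criterion refers to a level. Its wording could also mean a change from baseline, which would widen the gap.

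The documents give no rate for such events, and few are expected. With so few subjects, however, one omitted case would matter to the table. SAP 5.1 curtails only the efficacy analyses, so the safety tables are still due.

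**What to change.** In SAP 5.2.3:
- Report ALT or AST ≥ 3 × ULN, bilirubin ≥ 2 × ULN, and their combination against fixed ULN for all subjects, whatever the baseline.
- Flag every subject who meets any Protocol 5.4.1.1 criterion and name the criterion. INR, symptoms and adverse events are already collected.
- Keep the baseline-multiple rule as a separate, labelled row.
- State that the parenthesis means substitution, and whether the bilirubin criterion is a level or a change.

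A separate row for the 5.4.1 reporting threshold would add little to capture.

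The cost is a few table rows and one flag in the listing. The drawback is that children with stable pre-existing elevation will appear in the fixed-ULN rows; the baseline-multiple row tells them apart. This changes reporting only and proposes nothing about the clinical stopping limits.
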